9.2 Criteria for Evaluation: Chronic Myeloid Leukemia (CML)

Response will be evaluated in this study using the recommendations of the City of Hope CML Disease Committee. The following categories from the Revised Recommendations of the International Working Group will be used:

Morphologic complete remission (CR): The patient must satisfy the following conditions:

- a. WBC < 10,000/ul
- b. Hemoglobin > 11.0 gm/dl
- c. Platelet count < 500,000/ul
- d. No immature cells in peripheral blood
- e. No palpable splenomegaly

Cytogenetic complete remission (CRc): The patient must have 0% Ph+ metaphases (when a minimum of 20 cells are analyzed) or < 1% by FISH* (minimum of 200 cells analyzed). (Note*: For outside institutions conducting FISH analysis, note background for outside institution.)

Molecular complete remission (CRm): The patient must have no detectable bcr-abl mRNA by RT-PCR.

Morphologic partial remission (PR): The patient must satisfy one or more of the following conditions:

- a. WBC > 10,000/ul but < 50,000/ul and 50% below pretreatment values
- b. Hemoglobin > 9.0 but < 11.0 gm/dl
- c. Platelet Count > 500,000/ul
- d. Differential > 1% precursor cells
- e. Palpable splenomegaly
- 9.3 Treatment Failure:

Resistant disease: Patient does not achieve CR or PR upon repeat bone marrow examination after transplant, persistent leukemia in blood or bone marrow.

Aplasia: Patient dies, death occurs while cytopenic with aplastic bone marrow.

Indeterminate cause: Patient dies with no blasts in peripheral blood but no bone marrow examination.

Morphologic relapse: Reappearance of blasts post-CR in peripheral blood or bone marrow.

Molecular or cytogenetic relapse: Reappearance of the molecular or cytogenetic abnormality.

- 9.4 Endpoint Definitions:
 - a. Overall survival. Defined as the time from transplant to death due to any cause. If a patient is alive, survival time is censored at the time of last follow-up.
 - b. Relapse-free survival. Defined as the time from transplant to the first observation of relapsed disease or death due to any cause, whichever occurs first. If the patient has not relapsed or died, relapse-free survival is censored at the time of last follow-up.
 - c. Event-free survival. Defined as the time from transplant to treatment failure or death due to any cause, whichever occurs first. If the patient has not experienced an event of interest or died, event-free survival is censored at the time of last follow-up
 - d. Remission duration. Defined as the time from transplant to the first observation of relapsed disease. (Note: Morphologic, molecular and cytogenetic remission duration will be calculated separately.)

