4.1 Definition of Disease Phases in Chronic Myeloid Leukemia

Chronic Phase

- 1. No significant symptoms, which are not readily controlled by conventional doses of hydroxyurea or busulfan.
- 2. None of the features of accelerated phase or blastic phase. (Note: Granulocytic hyperplasia and the Philadelphia chromosome may be present in the bone marrow).

Accelerated Phase (any one or more of the following criteria)

- 1. White blood count (WBC) difficult to control with conventional use of busulfan/hydroxyurea in terms of doses required or shortening of intervals between courses.
- 2. Rapid doubling of WBC (\leq 5 days).
- 3. \geq 10% blasts in blood or marrow.
- 4. \geq 20% blasts plus promyelocytes in blood or marrow.
- 5. \geq 20% basophils plus eosinophils in blood.
- 6. Anemia or thrombocytopenia unresponsive to busulfan/hydroxyurea.
- 7. Persistent thrombocytosis (≥ 1,000,000/ 1) unresponsive to conventional doses of hydroxyurea or busulfan.
- 8. Additional chromosome changes (evolving new clone).
- 9. Increasing splenomegaly unresponsive to conventional doses of hydroxyurea or busulfan.

- 10. Development of chloromas or myelofibrosis.
- 11. Patients in a second (or subsequent) chronic phase after blast crisis.

Blastic Phase/Blast Crisis

1. \geq 30% blasts plus promyelocytes in the blood or bone marrow.

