5.0 ELIGIBILITY CRITERIA

- 5.1 Inclusion Criteria
 - 5.1.1 Patients with the following diagnoses are eligible for this study:
 - advanced myeloid malignancies with a disease status of >2nd remission, induction failure, or relapse
 - chronic myeloid leukemia in blast crisis
 - myelodysplasia, subtype: refractory anemia with excess blasts (RAEB)
 - 5.1.2 All candidates for this study must have a HLA (A, B, C, DR) identical sibling who is willing to donate bone marrow or primed blood stem cells or a 10/10 allele matched unrelated donor or minor mismatches as per BMT SOP that allows Tacrolimus and Sirolimus to be given for GVH prophylaxis. All ABO blood group combinations of the donor/recipient are acceptable since even major ABO compatibilities can be dealt with by various techniques. (Red cell exchange or plasma exchange).
 - 5.1.3 Prior therapy with VP-16, busulfan, hydrea and gleevec are allowed.
 - 5.1.4 Patients must be older than 6 years and the upper age limit for this study is 55 years.
 - 5.1.5 A cardiac evaluation with electrocardiogram and MUGA or echocardiogram is required for all patients. Patients must have an ejection fracture of greater than or equal to 50%.
 - 5.1.6 Patients must have a serum creatinine of less than or equal to 1.2 or creatinine clearance > 80ml/min.
 - 5.1.7 A bilirubin of less than or equal to 1.5. Patients should also have an SGOT and SGPT less than 5 times the upper limit of normal.
 - 5.1.8 Pulmonary function tests including DLCO will be performed. FEV $_1$ and DLCO should be greater than 50% of predicted normal value.
 - 5.1.9 Time from the end of last induction or reinduction attempt should be greater than or equal to 21 days.
 - 5.1.10 A signed (IRB approved) informed consent document is required. The patient, donor family member, and transplant team (physician, nurse, and social worker) meet together at least once prior to starting the transplant procedure to review all

pertinent risk/benefit information as part of the consenting process. Alternative treatment modalities are also discussed at this meeting.

- 5.2 Exclusion Criteria
 - 5.2.1 Prior radiation therapy/exposure that prevents the patient from receiving IMRT. (Determination will be made by the Radiation Oncologist.)
 - 5.2.2 Patients who have previously undergone a blood/marrow transplant and now have relapsed disease.

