9.0 CRITERIA FOR EVALUATION AND ENDPOINT DEFINITIONS

9.1 Criteria for Evaluation: Acute Myeloid Leukemia (AML) and Myelodysplasia (MDS)

Response and progression will be evaluated in this study using the Revised Recommendations of the International Working Group for Diagnosis, Standardization of Response Criteria, Treatment Outcomes, and Reporting Standards for Therapeutic Trials in Acute Myeloid Leukemia [JCO 21:4642-4649, 2003]. The following categories from the Revised Recommendations of the International Working Group will be used:

Morphologic leukemia-free state: Less than 5% blasts in an aspirate sample with marrow spicules and with a count of at least 200 nucleated cells. There are no Auer rods or persistence of extramedullary disease. (The presence of a unique phenotype by flow cytometry identical to what was found in the pre-treatment specimen is viewed as persistence of leukemia.)

Morphologic complete remission (CR): The patient achieves the morphologic leukemiafree state and has an absolute neutrophil count of >1000/uL and a platelet count \geq 100,000/uL. The patient is independent of blood transfusions. No duration of response is required to fulfill these criteria.

Cytogenetic complete remission (CRc): Patients who achieve a morphologic CR along with reversion to a normal karyotype by cytogenetic analysis. For patients who have unique markers by routine cytogenetics or by FISH upon enrollment, these markers will be followed on subsequent bone marrow examinations using the same technique(s) to evaluate for CRc.

Molecular complete remission (CRm): Patients who achieve a morphologic CR with no residual disease by molecular or flow cytometic detection methods. For patients with unique multi-dimensional flow cytometry markers at the time of enrollment, these will be repeated on subsequent bone marrow studies to evaluate for CRm.

Morphologic CR with incomplete blood count recovery (Cri): Patient fulfills the criteria for morphologic CR except for residual neutropenia (<1000/uL) and/or thrombocytopenia (<100,000/uL).

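### Morphologic CR in CML has no marrow criterion and can contradict the resistant-disease rule in section 9.3

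*Combined protocol and SAP*

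**What the plan says.** Section 9.2 lists five conditions for morphologic CR in CML: a white count below 10,000/ul, "Hemoglobin > 11.0 gm/dl", "Platelet count < 500,000/ul", "No immature cells in peripheral blood" and "No palpable splenomegaly". Cytogenetic and molecular remission (CRc, CRm) are separate categories.

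Section 5.1.1 admits CML only as "chronic myeloid leukemia in blast crisis". Section 4.1 sets the threshold for that phase at "30% blasts plus promyelocytes in the blood or bone marrow", so a patient can qualify on the marrow alone.

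For AML and MDS, section 9.1 builds CR on a leukemia-free marrow, "Less than 5% blasts in an aspirate sample with marrow spicules and with a count of at least 200 nucleated cells", and adds floors for neutrophils and platelets and independence from transfusion.

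Section 9.3 applies to all diseases and defines resistant disease as: "Patient does not achieve CR or PR upon repeat bone marrow examination after transplant, persistent leukemia in blood or bone marrow". Section 9.4 makes treatment failure an event for event-free survival (EFS). Section 10.4 lists EFS among the primary endpoints and plans one combined efficacy analysis. Section 10.1 says that all disease responses will be reported.

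**The concern.** Every CML patient enters in blast crisis, and that diagnosis may rest on the marrow. A CR definition that never looks at marrow morphology cannot show that the blast crisis has cleared. White cells and platelets have upper limits only. That suits a disease with high counts, but not a patient recovering from a myeloablative transplant, whose counts may be very low for other reasons.

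Section 9.3 then judges CR or PR at a repeat marrow examination, although marrow morphology plays no part in the CML definition of CR. The label feeds the reported responses, morphologic remission duration and, through treatment failure, EFS. In a combined analysis, one CR category would hold patients held to two quite different standards.

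**Working it through.** **1. The two CR definitions side by side**

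| Item | CML (9.2) | AML/MDS (9.1) |
|---|---|---|
| Marrow blasts | none stated | below 5%, adequate aspirate |
| Extramedullary disease | palpable spleen only | must be absent |
| White cells / neutrophils | WBC below 10,000/ul; no floor | ANC above 1000/uL |
| Platelets | below 500,000/ul; no floor | at least 100,000/uL |
| Hemoglobin | above 11.0 gm/dl | none stated |
| Transfusion independence | not required | required |
| Blood blasts | no immature cells | not listed separately |

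**2. The rules applied to hypothetical patients.** The values are assumed. They test the wording and say nothing about frequency. None of the four has a palpable spleen.

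| Patient | Blast crisis by 4.1 | CR by 9.2 | Leukemia persisting by 9.3 |
|---|---|---|---|
| A: marrow blasts 80%, none in blood, WBC 3,000, Hb 11.5, platelets 40,000 | yes | yes | yes |
| B: as A, but Hb 9 | yes | no | yes |
| C: as A, but 30% blasts in blood | yes | no | yes |
| D: empty marrow, WBC 100, platelets 5,000, Hb 11.5 (possibly transfused) | no | yes | no |

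Section 9.3 gives no blast threshold for persistence. I used 5% as an assumption; at 80% the choice does not matter. Patient A is the contradiction. Patients B and C show what limits it: the hemoglobin floor and the blood-blast item. Patient D shows the effect of the missing floors. The aplasia category in 9.3 does not catch D, because it applies only when the patient dies.

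**3. Two readings of the resistant-disease sentence.** If the words after the comma are a criterion of their own, patient A is both in CR and a treatment failure, and EFS has an event. If they only explain what failing CR or PR means, patient A is in CR and has no EFS event before death or a later failure. The protocol does not choose between these.

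**4. Relapse and relapse-free survival (RFS).** Morphologic relapse in 9.3 requires blasts to come back after a CR. In patient A they never left. Under 9.2 as written, there is a CR but no reappearance. With the 9.1 requirements added, there is no CR for a relapse to follow. Neither version records a relapse, so relapse rate and RFS do not differ for such a patient.

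**5. Scale.** The plan gives no figure for this definition. Its only related number is the phase II precision in 10.2, which reproduces: s.e. = sqrt(0.5 × 0.5 / 30) = 0.0913, and 1.96 × 0.0913 = 0.179, matching the stated 9.1% and 18%. One reclassified patient moves a proportion by 1/30 = 3.3 points, or 1/36 = 2.8 points if six phase I patients at the MTD are included. If 1 to 4 of 36 patients had CML and all were misclassified, the shift would be 2.8 to 11.1 points (4/36). That range is an assumption and a ceiling. It applies to a CR proportion or, on one reading of 9.3, an EFS proportion.

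**The case against.** The strongest reply is that 9.3 already covers the case: its closing words count leukemia persisting in the marrow as resistant disease, so EFS can capture patient A. This stands in part. It means that one cannot say the EFS event is lost, only that it depends on the reading. It does not remove the conflict with 9.2, and it does nothing for patient D.

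A reader might infer that false CRs hide relapses and flatter relapse rate and RFS. The documents do not support this. By step 4, never-cleared blasts produce no relapse event with or without the correction, and 9.3 treats AML the same way. Any gap there lies in the relapse definition.

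A reader might also infer harm from the fact that patient A meets CR at enrollment. No endpoint in 9.4 uses CR status at entry; all run from transplant, and eligibility rests on 4.1 and 5.1.1.

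Two further replies are fair. The conflict needs marrow-only blasts, hemoglobin above 11.0, the other counts under their ceilings and no palpable spleen, all together, and the protocol does not say how common that is. CRc and CRm could also expose residual disease, and remission duration is calculated separately by type. But neither category is a condition for morphologic CR, so the morphologic label stands.

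Finally, 9.2 cites the institution's CML committee, whose recommendations are not in the protocol. They may contain a marrow item; the criteria as written do not.

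**Conclusion.** The point holds as a faulty response definition. Followed as written, 9.2 can place a CML patient in CR whom 9.3 calls resistant, with no rule of precedence, and can also score CR on an empty marrow with minimal counts. The effects are on reported CML responses, on morphologic remission duration (if it is computed for patients labeled as in remission), and on EFS according to how 9.3 is read. CR also means something different in CML than in AML/MDS within one analysis.

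The size cannot be computed, because the protocol gives neither the number of CML patients nor how often the required profile occurs. It may be small. The point is worth acting on because one of the affected endpoints is named as primary in 10.4 and the correction needs only wording. The conclusion rests on the text of 4.1, 5.1.1, 9.1, 9.2 and 9.3, not on the assumed patient numbers.

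**What to change.** For CML transplanted in blast crisis, add to the 9.2 morphologic CR the response requirements already in 9.1: marrow blasts below 5% on an adequate aspirate, no extramedullary disease, ANC above 1000/uL, platelets at least 100,000/uL, and transfusion independence. Keep the no-splenomegaly item, and keep CRc and CRm as they are. In 9.3, state that leukemia persisting in the marrow is resistant disease whatever the blood counts.

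Assess CR at the marrow examinations that the study calendar (Appendix V) already schedules at day 30, day 100 and yearly. No test is added.

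The cost is that fewer CML patients will be called CR, so the reported response may look slightly less favorable. One consequence should be settled in the same edit. Section 9.2 has no counterpart to the 9.1 category for CR with incomplete count recovery. The text should say how a CML patient with a clear marrow but low counts is classed, so that such a patient does not become resistant disease by default.

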10.4 Analysis of Clinical Endpoints

There will be one combined statistical analysis for efficacy. In accordance with the primary study objectives, we will perform descriptive statistical analyses on these data after the phase II study is complete. Our primary endpoints will be OS, RFS, EFS, TRM, and RR with infection and acute- chronic- GVHD as secondary endpoints. Confidence Intervals will be estimated by calculating exact 95% confidence limits for a binomial parameter. The time-to-event endpoints, such as RFS and OS, will be estimated using the product limit method of Kaplan-Meier and tested using the Log-Rank test.

11.0 REGISTRATION GUIDELINES

Once a signed informed consent has been obtained and all pre-treatment evaluations have been performed, patients will be entered on study after review of patient eligibility criteria by the assigned Clinical Research Associate from the City of Hope Department of Biostatistics. Patients may be screened for registration by calling the Department of Biostatistics at [name].

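### CML partial remission in 9.2 is met by any one of five listed findings, four of which need no improvement, so unchanged blast-crisis disease can be labelled PR and, on one reading of 9.3, produce no EFS event before death

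*Combined protocol and SAP*

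**What the plan says.** Section 9.2 gives two morphologic response categories for CML. CR lists five conditions with nothing to suggest that fewer than all five will do. PR lists five conditions under the rule "The patient must satisfy one or more of the following conditions".

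Section 9.3 lists the forms of treatment failure. Resistant disease opens with "Patient does not achieve CR or PR upon repeat bone marrow examination after transplant". After a comma, and with no connecting word, it adds a clause on leukemia that persists in blood or marrow. Morphologic relapse is blasts coming back after a CR. Molecular or cytogenetic relapse is the abnormality coming back.

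Section 9.4(c) gives event-free survival as "Defined as the time from transplant to treatment failure or death due to any cause", and 10.4 states: "Our primary endpoints will be OS, RFS, EFS, TRM, and RR". Section 10.1 adds that all disease responses will be reported, so the PR label will itself appear in the results.

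CML patients enter only in blast crisis (5.1.1), which 4.1 defines as at least 30% blasts plus promyelocytes in blood or marrow.

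**The concern.** A partial-remission category should separate patients who improved from those who did not. Here the list mostly describes what may still be abnormal, and the combining rule makes each abnormality sufficient by itself. A patient can therefore be PR because of residual disease and not because disease was reduced.

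PR is not itself an endpoint, but it decides whether an EFS event exists, because 9.3 exempts PR patients from resistant disease. If the exemption is applied literally, a CML patient whose leukemia never cleared stays event-free until death. EFS would then look better than it is, and the reported PR count would include non-responders.

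**Working it through.** The plan states no figure on this point, so there is nothing to reproduce. The check applies the 9.2 rules as written and follows the result through 9.3 and 9.4.

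**Step 1. The CML conditions side by side (9.2).**

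| Item | CR (all required) | PR (any one suffices) | Does PR need improvement? | Upper limit in PR? |
|---|---|---|---|---|
| a. White count | below 10,000 | "WBC > 10,000/ul but < 50,000/ul and 50% below pretreatment values" | yes | yes |
| b. Hemoglobin | above 11.0 | "Hemoglobin > 9.0 but < 11.0 gm/dl" | no | range only |
| c. Platelets | below 500,000 | "Platelet Count > 500,000/ul" | no | none |
| d. Immature cells | none in blood | above 1% | no | none |
| e. Spleen | not palpable | palpable | no | none |

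PR items (c) to (e) are close to the reverse of the matching CR items. None of the five refers to the marrow. By contrast, PR for AML and MDS in 9.1 requires CR-level blood values and a fall of at least 50% in the marrow blast percentage, to 5-25%.

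**Step 2. One patient with active disease.** Take white count 120,000, hemoglobin 8, platelets 700,000, 60% circulating precursors (counting blasts as precursors, an assumption) and a palpable spleen. Items (a) and (b) fail; (c), (d) and (e) are met. One would be enough, so the label is PR.

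**Step 3. How general this is.** The rules were applied to a grid of hypothetical profiles: white count 6,000, 20,000, 45,000, 60,000 or 120,000; hemoglobin 12, 10 or 8; platelets 200,000 or 700,000; precursors 0, 0.5, 5 or 60%; spleen palpable or not; pretreatment white count assumed to be 80,000. That gives 5 × 3 × 2 × 4 × 2 = 240 profiles.

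- CR: 1. PR: 224. Neither: 15.
- Profiles with 60% precursors: 60, all of them PR.
- If all five items were required instead of any one, only 2 of the 240 would be PR.

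These counts show how the rule behaves. They are not patient frequencies, and requiring all five is not a usable definition, because it would make a palpable spleen and high platelets compulsory for PR.

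**Step 4. Trace to EFS for the patient in step 2.**

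- Resistant disease, first part: not met, because the patient is PR.
- Morphologic relapse: not met, because there was no CR.
- Molecular or cytogenetic relapse: not met, because the abnormality never disappeared.
- The two remaining failure categories in 9.3 (aplasia, indeterminate cause) both require death.
- Resistant disease, trailing clause: met if it stands as a separate criterion, not met if it only describes patients already outside CR and PR. The sentence does not say which.

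On the second reading, death is the only EFS event left.

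**Step 5. Size.** Section 10.2 plans 30 additional adults at the MTD. Section 7.3 includes all patients accrued at the MTD, so with six from phase I the total is 30 + 6 = 36. With complete follow-up to the time at which EFS is quoted, one patient counted event-free instead of failed moves the proportion by 1/n:

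- n = 30: 1/30 = 3.3 points; 2/30 = 6.7; 3/30 = 10.0.
- n = 36: 1/36 = 2.8 points.

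The shift occurs only if the patient is alive at that time. If the patient has already died, death is the EFS event and the proportion at that time does not change; the event is only dated later.

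**The case against.** The strongest reply is the trailing clause in 9.3. A patient with blasts in the blood plainly has persistent leukemia. If the clause is a criterion in its own right, that patient is an EFS failure whatever the PR label says, and no bias arises. This has real weight, and it rules out saying flatly that such patients escape the event. It does not dispose of the point. The clause has no connecting word. Read as independent, it nearly empties the PR exemption in the same sentence, since AML/MDS PR normally leaves 5-25% marrow blasts. It also leaves the 9.2 definition wrong. Two analysts could classify the same patient differently, and each could cite the text.

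The second reply is that the consequences are limited, and this stands. Section 10.2 names relapse rate and grade 3-5 mucositis as the phase II primary endpoints and sizes the trial on relapse rate. EFS is primary only in the 10.4 list, where the analysis is descriptive, and no stopping rule uses it. OS, RFS, TRM and relapse rate do not depend on the PR label.

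A reader might infer two stronger things that the documents do not support. One is that any abnormal finding gives PR: a white count of 50,000 or more alone, or hemoglobin of 9.0 or less alone, does not qualify. The other is a bias of a definite size, such as 3 to 11 points for one to four patients among 36 (4/36 = 11.1%). The plan gives no CML count, and that range assumes every affected patient is alive at the time point. It is a ceiling and not an estimate.

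**Conclusion.** The CML PR definition is wrong as written. Any one of five listed findings suffices, (b) to (e) require no improvement, and (c) to (e) are unbounded signs of residual disease. Combined with 9.3, it allows a blast-crisis patient with unchanged disease to be PR and to have no EFS event before death. Whether that happens depends on how the trailing clause of 9.3 is read, and the text leaves this open.

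The effect is confined to CML patients in blast crisis. It is at most 3.3 points per affected surviving patient on an adult EFS proportion at n=30, or 2.8 at n=36, assuming complete follow-up to the time quoted. The total cannot be estimated from the documents. This should be corrected because it sits in the definition of an endpoint that 10.4 calls primary and the correction is cheap. It does not threaten the sample size or the safety rules.

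**What to change.** 1. In 9.2, reword CML PR so that it requires improvement from pretreatment, including a reduction in blasts or precursors parallel to the AML/MDS PR in 9.1. List (b) to (e) as residual abnormalities that a PR patient may still have, not as conditions that confer PR.

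2. Do not simply make (a) compulsory in its present words. Its floor of 10,000 excludes a patient whose white count has returned to normal. A patient starting at 20,000 or less could never qualify, since a 50% fall gives 10,000 or less. It would also still admit a patient whose count fell from 100,000 to 45,000 with 60% blasts.

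3. In 9.3, state that for CML, leukemia persisting in blood or marrow counts as resistant disease whatever the PR label. This is better than removing PR from the CML failure rule altogether, which would class a patient whose only abnormality is hemoglobin 10.5 as resistant, because CR requires more than 11.0.

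The cost is a sentence or two in each section. Blood counts, differentials and marrow examinations are already in the Appendix V calendar, so no new data are needed. The downside is that a few CML patients may be counted as EFS failures earlier, making EFS slightly less favorable.
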